10.4 Analysis of Secondary Endpoints

All secondary endpoints will be analyzed in the ITT population.

The proportion of participants experiencing adverse events (AE) events will be summarized by AE type and treatment arm. The proportion of participants experiencing an AE will be calculated as the number of participants who have experienced an AE divided by the number of participants in the ITT population. AEs will be summarized by each arm separately. AEs may be compared by arm using a Fisher's exact test.

The proportion of participants experiencing serious adverse events (SAE) events will be summarized by SAE type and treatment arm. The proportion of participants experiencing an SAE will be calculated as the number of participants who have experienced a SAE divided by the number of participants in the ITT population. SAEs will be summarized by each arm separately. SAEs may be compared by arm using a Fisher's exact test.

The baseline, follow-up, and change from baseline in mPAP, 6MWDT, EMPHAIS-10 score, SGRQ score, serum HA concentration, and NT-proBNP will be summarized using means, standard deviations numbers of observations, and 95% confidence intervals for each randomization arm. Differences in these measures may be calculated between the treatment and placebo group overall and within different types of PH (e.g. Group 1 versus Group 3) to assess treatment differences.

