9	MONITORING AND REPORTING OF ADVERSE EVENTS	25
9.1	Adverse Events Definition.....	25
9.2	Suspected Adverse Reaction Definition	25
9.3	Serious Adverse Event or Serious Adverse Reaction Definition.....	25
9.4	Unexpected Adverse Event or Reaction Definition.....	25
9.5	New Fact	26
9.6	Identification of Adverse Events	26
9.7	Follow-up of Adverse Events	27
9.8	Guidelines for Assessing Severity of an Adverse Event.....	27
9.9	Guidelines for Determining Causality	27
9.10	Serious Adverse Events	28
9.11	Unexpected Non-serious Adverse Events.....	28
9.12	Reporting to Health Authority	28
9.12.1	Standard Reporting (IND Annual Report).....	28
9.12.2	Expedited Reporting	28
9.13	Protocol Violations	29
9.14	Reasons for Early Termination	29
9.14.1	Halting the Study	29
9.15	Data Safety Monitoring.....	30
10	STATISTICAL METHODS AND CONSIDERATIONS.....	30
10.1	Analysis Population	30

The SATURN Study [CONFIDENTIAL – DO NOT REDISTRIBUTE]

10.2	Descriptive Statistics.....	30
10.3	Analysis of Primary Endpoints	31
10.4	Analysis of Secondary Endpoints	31
10.5	Analysis of Exploratory Endpoints	31
10.6	Missing Data Handling	32
10.7	Sample Size and Randomization	32
11	DATA COLLECTION, RETENTION AND MONITORING	32
11.1	Data Collection Instruments	32
11.2	Data Management Procedures	33
11.3	Data Quality Control and Reporting.....	33
11.4	Archival of Data.....	33
11.5	Availability and Retention of Investigational Records	34
11.6	Subject Confidentiality	34
12	ETHICAL CONSIDERATIONS	34
12.1	IRB and HIPAA.....	34
12.2	Potential Participant Risks	36
12.3	Potential Benefits	36
13	Abbreviations	36
14	References.....	37

1 **BACKGROUND**

1.1 **Introduction**

This is a prospective, randomized, double-blind, study of H01 of 24 weeks in adults with pulmonary hypertension (PH) with an optional open-label extension (extension to 48 weeks). The primary objective of this double-blinded study is to evaluate the clinical efficacy of H01 over 24 weeks. Secondary objectives are to investigate the safety and tolerability of H01 and pharmacokinetic (PK) and pharmacodynamic (PD) markers in this population. Following IRB approval and written informed consent, a total of 16 participants will be enrolled, randomized approximately 2:1 (H01 1600 mg/day : placebo), stratified by PH type, and treated for 24 weeks. Data from this study will inform future larger studies. Participants will have the opportunity to extend their participation an additional 24 weeks by consenting to an open-label extension.

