2.6 Hypothesis

We hypothesize that oral H01 at doses of 1600 mg per day for 24 weeks in the blinded study and for an additional 24 weeks as part of open-label extension will be safe and well-tolerated and show evidence of clinical efficacy. We will conduct exploratory analyses in both the blinded study and open-label extension to further establish the correlation of changes in serum HA with meaningful clinical outcomes.

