10.2 Descriptive Statistics

Descriptive statistics will be reported for all key participant variables, including, but not limited to,

baseline clinical and demographic characteristics, use of medications, laboratory values, vital signs, clinical outcomes, adverse events, compliance, and study completion status. Proportions will be presented for categorical variables. Continuous variables will be presented using means, standard deviations, and number of observations if the data are normally distributed. If the data are not normally distributed, then continuous variables will be presented using medians and interquartile ranges. In all cases, between-group comparisons will be assessed using absolute standardized differences.

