10.7 Sample Size and Randomization

A total of 16 participants with PH will be enrolled in the study. Participants will be randomized 5:3 to treatment:placebo. Randomization will be stratified by PH type. As no formal hypothesis testing will be performed on the primary endpoint, this sample size is not based on a statistical powering. However, data on hand regarding clinical improvement and HA changes in preclinical and clinical settings suggests we will be able to draw meaningful insights from a study of this size that informs future trials.

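### Section 10.4 gives adverse event proportions no confidence interval, and the one between-arm test it names, an optional Fisher's exact test, says little about safety at 10 v 6

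*Combined protocol and SAP*

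**What the plan says.** Section 4.2 lists safety and tolerability, graded by CTCAE, first among the secondary endpoints. Section 2.6 hypothesises that H01 "will be safe and well-tolerated and show evidence of clinical efficacy".

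Section 10.4 commits to proportions of participants with AEs and with SAEs, by event type and by arm, in the ITT population. It then adds "AEs may be compared by arm using a Fisher's exact test" and, for serious events, "SAEs may be compared by arm using a Fisher's exact test". It states no significance level, sidedness or decision rule, and no interval for a proportion or for a difference. The same section gives every continuous secondary endpoint a 95% confidence interval. Section 10.3 does so for the primary endpoint and rules out hypothesis testing there.

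Section 10.2 also covers safety. Its list of variables includes "laboratory values, vital signs, clinical outcomes, adverse events, compliance, and study completion status", and it says "In all cases, between-group comparisons will be assessed using absolute standardized differences".

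On size, Section 10.7 says "A total of 16 participants with PH will be enrolled in the study" and "Participants will be randomized 5:3 to treatment:placebo", and that the number does not rest on a power calculation. Section 1.1 gives a different ratio: "randomized approximately 2:1 (H01 1600 mg/day : placebo), stratified by PH type".

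**The concern.** In Sections 10.3 and 10.4, AEs and SAEs are the only outcomes offered a p-value and given no interval. With arms this small, the p-value answers the less useful question. A trial meant to inform larger studies needs to state how large an excess risk remains compatible with its data. A list of non-significant p-values by event type does not show that, and a reader could take it as showing no safety difference. The summary in Section 10.2 does not supply it either. An absolute standardized difference drops the sign, so an excess on placebo looks like an excess on H01. It has no measure of uncertainty, and it is undefined (0/0) when neither arm has an event, which is where an upper limit is most needed.

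**Working it through.** The plan states no power, significance level or detectable difference for AEs, so there is no planned figure to reproduce.

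**Inputs.** N = 16 and 5:3 allocation, from Section 10.7. Arms: 16 × 5/8 = 10 on H01 and 16 × 3/8 = 6 on placebo. Two-sided 5% is an assumption.

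**Critical values.** With both margins fixed and t events in total, P(k events on H01) = C(10,k)·C(6,t−k)/C(16,t). The two-sided p sums all tables no more probable than the one observed.
- 5/10 v 0/6: t = 5, and the qualifying tables are k = 5, 1 and 0. p = (252 + 150 + 6)/4368 = 0.093.
- 6/10 v 0/6: t = 6, and the qualifying tables are k = 6, 1 and 0. p = (210 + 60 + 1)/8008 = 0.034.

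| Placebo events | Fewest H01 events for p < 0.05 | p |
|---|---|---|
| 0/6 | 6/10 | 0.034 |
| 1/6 | 8/10 | 0.035 |
| 2/6 | 9/10 | 0.036 |
| 3/6 | 10/10 | 0.036 |

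With four or more placebo events, no excess on H01 reaches 5%. Below the first threshold, 4/10 v 0/6 gives p = 0.23 and 3/10 v 0/6 gives p = 0.25.

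**Power.** If the true placebo rate is 0%, power is P(X ≥ 6) for X ~ Binomial(10, p).

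| True H01 rate | Power, placebo 0% | Power, placebo 10% |
|---|---|---|
| 30% | 4.7% | 2.6% |
| 40% | 16.6% | not computed |
| 50% | 37.7% | 22.1% |
| 60% | 63.3% | 40.0% |
| 70% | 85.0% | 60.2% |

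The test is also conservative. Its actual two-sided type I error is 0.6%, 1.7% and 2.5% at common event rates of 10%, 20% and 30%.

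**Sensitivity to the allocation conflict.** 16 × 2/3 = 10.7, so roughly 2:1 means about 11 v 5. The threshold with no placebo events is then 7/11 (p = 0.034), and 6/11 gives p = 0.093. Power at 30% v 0% is 2.2% and at 40% v 0% is 9.9%. The conclusion is the same under either ratio.

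**What an interval would show.** For zero events in n, the Clopper-Pearson 95% upper limit is 1 − 0.025^(1/n).
- 0/10: 1 − 0.025^(1/10) = 30.8%.
- 0/6: 1 − 0.025^(1/6) = 45.9%.
- 4/10 v 0/6: the risk difference is 40 points, with a Newcombe 95% interval of −5% to +69%. Fisher reports only p = 0.23.

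**What the standardized difference shows.** It is |p₁ − p₂| / √{[p₁(1−p₁) + p₂(1−p₂)]/2}.
- 3/10 v 0/6: 0.30/√(0.21/2) = 0.93.
- 1/10 v 0/6: 0.10/√(0.09/2) = 0.47.

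A single event on H01 already gives 0.47, with nothing to say how uncertain that is.

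**The case against.** The best defence is that nothing depends on the test. Section 10.4 says twice that arms may be compared this way. It attaches no threshold and no safety conclusion. The committed output is proportions by type and arm, so readers will see the counts, and with 16 participants those carry most of the information. Action on safety during the trial rests on counts of adverse reactions and on committee review (Sections 9.14.1 and 9.15), not on a p-value. Low power comes from the sample size, and Fisher's test is a standard choice for sparse tables.

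Most of this stands, and it rules out three stronger readings that a reader might infer:
- *Fisher's test is the plan's only between-arm safety comparison.* It is the only test named in Section 10.4, but Section 10.2 also applies standardized differences to adverse events. At 3/10 v 0/6 these flag a large imbalance (0.93) where Fisher gives p = 0.25.
- *Non-significance is almost guaranteed unless 60% of H01 participants have an event absent on placebo.* Significance can also be reached with one to three placebo events, at higher H01 counts. With none on placebo, power is 63% to 85% at true H01 rates of 60% to 70%. The description fits rates up to about 30% to 40%.
- *The plan uses non-significance as false reassurance.* No section equates a non-significant result with safety, and the hypothesis in Section 2.6 is not tied to this test.

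The defence does not supply the missing interval. Pause rules govern conduct and not the final estimate, and counts alone leave readers to work out the uncertainty themselves.

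**Conclusion.** The point holds as a minor reporting gap. Section 10.4 gives no measure of uncertainty for AE or SAE proportions or their difference, and neither comparison in the plan supplies one. At 10 v 6 and an assumed two-sided 5% level, an excess on H01 cannot reach significance below 6/10. Power is about 5% at 30% v 0% and 17% at 40% v 0%, so non-significance would be weak evidence of safety. Misreading is a risk that the plan leaves open, not something it prescribes. These figures assume all 16 are randomized and analysed, as the ITT definition implies. They shift slightly, in the same direction, at about 11 v 5.

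**What to change.** In Section 10.4:
- Report each AE and SAE proportion, per arm, with an exact (Clopper-Pearson) 95% interval. Where an arm has no events of a type, give the upper limit.
- Report the H01-minus-placebo risk difference with a small-sample 95% interval, such as Newcombe, labelled descriptive and unadjusted for multiplicity.
- Make these the safety comparison in place of the Fisher p-values. Alternatively, keep any Fisher p-value as secondary, with a sentence that non-significance is not evidence of safety.

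Align Section 10.2 with Section 10.4 so that one between-arm method is named for adverse events. Reconcile the allocation ratio between Sections 1.1 and 10.7.

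The cost is a few sentences and one table shell, with no change to trial conduct. There are two downsides. The intervals will be wide, which is accurate. Approximate difference intervals can also exclude zero where Fisher does not reach 5%: at 5/10 v 0/6 Newcombe runs from +2.9% to +76.3% while Fisher gives p = 0.093. The text should therefore say that the intervals are not to be read as tests.

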10.5 Analysis of Exploratory Endpoints

All exploratory endpoints will be analyzed in the ITT population and will be analyzed after all participants have completed treatment or have withdrawn from the trial.

The baseline, follow-up, and change from baseline in inflammatory markers, pro-inflammatory cytokines, PFTs (including FEV1, FVC, TLC, and DLCO), and EBC HA concentration, and HA fragment size will be summarized using means, standard deviations numbers of observations, and 95% confidence intervals for each randomization arm. Differences in these measures may be calculated between the treatment group, placebo group, and different types of PH (e.g. Group 1 versus Group 3) to assess treatment differences. The pharmacokinetics and fragment size will be described. There will also be a sensitivity analysis to investigate whether drug product used (Isochol vs Cantabiline) led to differential primary endpoint outcomes, using a stratified analysis by drug product.

10.6 Missing Data Handling

While we expect minimal missing data, it is inevitable in clinical trials. We will thoroughly and transparently present the amount of missing data for each variable where missing data is present. Given the small sample size, we will use complete case analyses.

10.7 Sample Size and Randomization

A total of 16 participants with PH will be enrolled in the study. Participants will be randomized 5:3 to treatment:placebo. Randomization will be stratified by PH type. As no formal hypothesis testing will be performed on the primary endpoint, this sample size is not based on a statistical powering. However, data on hand regarding clinical improvement and HA changes in preclinical and clinical settings suggests we will be able to draw meaningful insights from a study of this size that informs future trials.

11 DATA COLLECTION, RETENTION AND MONITORING

11.1 Data Collection Instruments

Data entry, database management, and data quality assurance will be led by a study coordinator at the study site. Source documentation will include site assessment forms, laboratory results, telephone surveys, and internet surveys. Where possible, electronic transfer of electronic source data to the study CRFs through a secure electronic data capture (EDC) system will be automated. Any paper-based forms that are used will be maintained in a secure locked facility at the study site and maintained by the site clinical research coordinator (CRC). An eCRF will ensure capture of information including subject identification, study identification, provision and date of informed consent form (ICF), visit dates, clinical results (safety and efficacy) as specified in the protocol, adverse events, concomitant medications, investigational medicine receipt/use/destruction, production administration, data of study completion, and reason for withdrawal if needed. The individual author of all source documents will be identifiable. Any adverse related reports will be signed off by the investigator. All study related documentation will employ the minimum of identifying information.

11.2 Data Management Procedures

In compliance with ICH/GCP guidelines, the study site will maintain all source documentation, CRFs, and study-related documents. All participants will be assigned a study ID. All study tools will use only the subject's study ID. Specimen containers and blood tubes for assignment to site laboratories or shipping to central laboratories will be labeled by the site CRC with the minimum amount of identifying information (e.g., participant identifier, study identifier, and date of collection).

A secure trial master file (TMF) maintained by qualified study staff and will include all study-related documents including the protocol, investigator brochure, study operations manual, statistical analysis plan, laboratory manual, email communications, SOPs, evidence of validated processes for ECD systems. Trial site-specific files will also be maintained on the TMF including a delegation of authority log, site roster for study personnel, qualified person certification, local SOPs affecting study conduct, ICF, and IRB approvals. The trial master file system will include audit trails for document versions and archiving capabilities.

11.3 Data Quality Control and Reporting

The lead investigator is responsible for ensuring that a roster of active study personnel is maintained, a delegation of authority log assigns tasks to individual team members, and that access to the secure study EDC and TMF systems are controlled in alignment with the roster and log.

In order to ensure data quality, quality audits will be performed. The timing of audits will be developed based on a risk-based approach, reflecting the nature of the study design, known profile of the drug being used, and patient population. Study monitors will follow an SOP. Elements of study monitoring will include:

1. Implementation of patient consent processes
2. Source data verification (SDV) (e.g., for questionnaires, hospital medical records, and biospecimen collections)
3. Pharmacy monitoring (drug accountability processes, IMP storage, labeling and expiry dates, randomization and blinding)
4. Laboratory monitoring (Adherence to Lab Manual and specimen handling requirements)
5. Adverse event reporting (ensuring reporting from source documents to trial team, reporting to local authorities)

The results of site audits will be shared with the clinical trial investigator(s) and IRB as appropriate.

11.4 Archival of Data

Electronic data including all study databases and supporting electronic documentation will be archived to

The SATURN Study [CONFIDENTIAL – DO NOT REDISTRIBUTE]

cloud-based servers on a daily basis.

11.5 Availability and Retention of Investigational Records

All electronic data will be kept in secured servers. All paper-based forms that are used will be maintained in a secure locked facility at the study site and maintained by the site CRC. Only the research team will have access to the data.

11.6 Subject Confidentiality

Participant medical and study information will be kept confidential. The following health information related to this study may be used or disclosed in connection with this research study, including, but not limited to, name and initials, address, email, phone number(s), date of birth, age, sex, race, ethnicity, medical record number, information related to COVID-19 disease, symptoms, physical exams, symptoms that might relate to medication side effects, vital signs including temperature and oxygen saturation levels, laboratory tests, pregnancy test, and medications received including study drug.

All participants will be given a sequential study ID. The code for this ID with personal identifiers will be maintained in a locked research file accessible only to study personnel. Only research personnel will have access to the research records. The data will be keyed into a secure study website in a coded fashion by the study coordinator. Paper research charts will be kept in a locked file cabinet with limited access. Laboratory personnel will have access to study specimens. The data is transferred by computer via password protected electronic network. When transferring via electronic networks, a password protected encrypted computer will be used.

12 ETHICAL CONSIDERATIONS

12.1 IRB and HIPAA

This study protocol, all procedures and informed consent forms (ICF), and any subsequent protocol amendments must be reviewed and approved by the Institutional Review Board (IRB). Prior to any study-related procedures, the investigator or designee will obtain from the participant a signed and dated written ICF consistent with FDA/ICH regulations and the HIPAA Privacy Rule. A HIPAA Privacy Rule Authorization language will be included in the ICF and must be IRB approved prior to study implementation. In addition, the document of Bill of Rights will be attached to the ICF so that the participants can read and understand the same. All versions will be maintained in the TMF.

12.2 Potential Participant Risks

H01: H01 is a natural active ingredient that is synthesized for pharmaceutical use. H01 is currently not FDA approved for use in the United States. However, H01 has been marketed and used as approved drug in Europe for >50 years (European Union reference date [EURD] 07/27/1965). Overall, H01 appears to be a safe and well-tolerated medication. The French product of H01 named Cantabiline will be used in

The SATURN Study [CONFIDENTIAL – DO NOT REDISTRIBUTE]

this trial. Cantabiline is authorized by the French Medicines Agency (Agence nationale de sécurité du médicament et des produits de santé (ANSM)) under CIP : 6 197 431 7. The recommended dose is 400 mg with main meals. The main side effect listed in the product label is the gastrointestinal pathology of diarrhea, which is listed as common 0.1% to 10%. Potential anaphylactic or allergic reactions are also listed as possible side effects with an unknown rate. The label recommends to not use in cases of biliary obstruction or severe hepatic impairment.

To minimize risks of potential severe allergic reactions, participants with a known allergy for H01 will be excluded. A standard operating procedure for managing allergic reactions, including anaphylaxis, will also be in place. These risks as well as guidance on the potential signs and symptom of a severe allergic reaction will be included in the participant consent. Additionally, if participants develop a grade 3 or higher allergic reaction thought to be due to the study drug, treatment with the study drug will be discontinued immediately. To minimize risks of gastrointestinal side effects, patients with acute biliary obstruction or severe hepatic impairment will be excluded from the study. Additionally, if participants develop diarrhea, we have developed guidelines based on diarrhea severity and participant preferences for 1) treating symptoms, 2) avoiding dose increases, 3) reducing doses, or 4) discontinuing treatment.

Right heart catheterization: RHC can cause bruising of the skin or infection at the site where the catheter (sterile tube) is inserted into a vein, injury to blood vessels, excessive bleeding because of puncture or damage to the vein during catheter insertion, or partial collapse of a lung if a neck or chest vein is used to insert the catheter. Rare but serious risks include abnormal heart rhythm or electrical blockage of heart beats, perforation of the heart muscle with bleeding into the sack around the heart, blood clots, stroke, heart attack, or death. Medications for pain or sedation can cause allergic reaction, an unconscious state, and depressed breathing. During the RHC, you maybe asked to perform an exercise test. With your feet on a supine ergometer you may exercise for 3 to 6 mins at a gentle pace. You may feel short of breath during this portion of the study. You can stop at any point.

Pulmonary function tests and expired breath condensate: PFTs and EBC are usually safe for most people. However, PFTs may require participants to breathe in and out quickly so they may feel dizzy and may faint.

Venipuncture & arterial blood gas: The risks of venipuncture and ABG include temporary discomfort, pain, and anxiety from the needle stick, bruising, and, rarely, infection. To minimize risk, all blood drawswill follow hospital/clinical procedures and be drawn by experienced providers. There is minimal risk regarding the blood loss related to study tests.

Privacy: There is a risk of loss of privacy around health information. To minimize this risk, information about participants will be handled with a goal of maintain confidentiality in compliance with privacy regulations (e.g. HIPPA and local government laws). Participant names and medical record numbers will be recorded for study management purposes. This information will not be included in the hard copy data case report forms or the electronic database used for data analysis and will be maintained in a locked filein a lockable office. It will not be disclosed to others. Study data will be identified by a unique study codefor each participant. Hard copy study data will be maintained in a separate locked research file in a lockable

The SATURN Study [CONFIDENTIAL – DO NOT REDISTRIBUTE]

office. The electronic data set, which will be identified by the unique study codes, will be keyed into a computer that is password protected and encrypted. Access to study data will be limited to research personnel who have completed protocol-specific training.

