5 STUDY POPULATION

Adults with Group 1 PAH secondary to connective tissue disease, idiopathic, hereditary, toxins, or drugs and adults with Group 3 PH secondary to interstitial lung disease. Individuals interested in participating in the study will be screened for inclusion and exclusion criteria. If the patient meets criteria and consents to participate, they will be enrolled and undergo randomization.

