- Subject is receiving $>10\text{L}/\text{min}$ of oxygen supplementation by any mode of delivery at rest at baseline
- Body mass index $\geq 40\text{kg}/\text{m}^2$
- Participants with history of dysphagia, achalasia, or difficulty swallowing capsules, tablets or pills
- Participants with liver failure or AST or ALT greater than 2 times the upper limit of normal
- Participants with total bilirubin levels greater than 2 times the upper limit of normal
- Participants with CrCl <45
- Use of any investigational drug/device, or participation in any investigational study with therapeutic intent within 30 days prior to randomization
- Known allergy to hymecromone or any component of drug product (including rare hereditary problems of galactose intolerance, Lapp lactase deficiency, or glucose-galactose malabsorption)
- Known allergy to any component of placebo (including rare hereditary problems of galactose intolerance, Lapp lactase deficiency, or glucose-galactose malabsorption)
- Physician concern that participant may not adhere to the study protocol
- Significant psychiatric, addictive, or other disorder that compromises the subject's ability to provide informed consent

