7 ASSESSMENTS

7.1 Screening/Baseline Assessment

Prior to enrollment, each participant will undergo a medical screen, be introduced to study procedures,

The SATURN Study [CONFIDENTIAL – DO NOT REDISTRIBUTE]

and undergo informed consent. Screening will be conducted within 30 days of baseline assessment. If any of the screening labs were performed as part of standard of care within 4 weeks of the screening, these labs will be used for screening.

If the patient qualifies and consents to participate, they will undergo baseline assessments. Baseline labs that were done within the previous 4 weeks will be accepted as baseline labs; if there are no labs for >4 weeks, these will be repeated. If any of the following baseline procedures were performed and documented in the medical chart at part of standard of care within 2 months of the baseline visit, these will be accepted as the baseline assessment: RHC, PFTs, 6MWDT, 12-Lead ECG.

All participants will start taking the study drug on the morning of Day 1, the day after the baseline assessment. All participants will follow up in person for assessments at Weeks 4, 12, and 24. Participants will also be contacted electronically and/or by telephone on Weeks 2, 8, 16, 20, 28. Participants will continue the study drug for 24 weeks with the final in person assessment at Week 24. A final follow-up electronically or by telephone will be performed at week 28 (4 weeks after treatment completion). If participants do not complete the 24 weeks of treatment for any reason, every effort will be made to conduct the Week 24 final assessment at the time of treatment termination and the participant will be followed until at least 4 weeks after stopping the study drug (longer if necessary to follow AEs). If the participants are enrolled in the open-label extension, they will be contacted by telephone on Weeks 26 and 36. A final in-person assessment will occur at Week 48.

Biological samples:

- Blood:
 - 6 ml blood for serum concentration of H01 and metabolites
 - 6 ml blood for serum HA level and biomarkers
 - 6 ml blood for CBC
 - 6 ml blood for CMP
- Urine:
 - Pregnancy test for females of child-bearing potential (serum pregnancy test may be substituted for urine)
- Exhaled breath condensate:
 - Concentration of HA levels, H01 and metabolites

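### Section 12.2 says patients with acute biliary obstruction are excluded, but neither 5.1 nor 5.2 lists that criterion, so screening could admit some of them

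*Combined protocol and SAP*

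**What the plan says.** Section 12.2 (Potential Participant Risks) names Cantabiline as the product to be used and reports its label: "The label recommends to not use in cases of biliary obstruction or severe hepatic impairment". It then gives a measure for limiting gastrointestinal side effects: "patients with acute biliary obstruction or severe hepatic impairment will be excluded from the study".

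Section 5 (Study Population) says how candidates are assessed: "Individuals interested in participating in the study will be screened for inclusion and exclusion criteria". In section 5.2 the hepatic criteria are two bullets: "Participants with liver failure or AST or ALT greater than 2 times the upper limit of normal" and "Participants with total bilirubin levels greater than 2 times the upper limit of normal". No bullet in 5.1 or 5.2 mentions biliary obstruction or any other biliary disease.

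Section 7.1 allows routine-care results to stand in for screening tests: labs "performed as part of standard of care within 4 weeks of the screening, these labs will be used for screening".

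**The concern.** Staff who screen candidates work from the criteria in section 5. An exclusion that appears only in the risk section can be missed, because nothing on the list prompts the screener to apply it. Two things are at stake.

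- **Safety oversight.** Under section 12.1 the IRB must review and approve the protocol. On this point it reads of a safeguard that the working list lacks.
- **Classification of participants.** Someone enrolled with acute biliary obstruction and laboratory values within the limits would breach 12.2 but no criterion in 5.2. Section 10.1 removes participants with major protocol deviations from the per-protocol population, and the two sections give different answers on whether any deviation occurred.

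The primary analysis is not affected. Section 10.3 analyses the primary endpoint in all randomized participants.

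**Working it through.** No arithmetic tests the main claim, which is about consistency of the text. There is no planned figure to reproduce either: section 10.7 states that "this sample size is not based on a statistical powering". The check compares what 12.2 promises with what the screening criteria contain.

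| Exclusion promised in 12.2 | Counterpart in 5.1 or 5.2 |
|---|---|
| Known allergy to H01 | Yes, its own bullet in 5.2 |
| Severe hepatic impairment | At least in part: liver failure, AST or ALT > 2 × ULN, total bilirubin > 2 × ULN |
| Acute biliary obstruction | None by name; only the same liver and laboratory criteria, which 5.2 does not link to obstruction |

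**Step 1: who is stopped.** A candidate with obstruction is excluded by 5.2 if liver failure is present, or if AST, ALT or total bilirubin exceeds 2 × ULN. Any one of these is enough.

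**Step 2: who is not stopped.** A candidate with obstruction, no liver failure, and all three tests at or below 2 × ULN on the accepted sample meets no exclusion criterion on this point.

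**Step 3: timing.** Under 7.1 the accepted routine-care sample may be 4 weeks (28 days) old at screening, and screening may fall up to 30 days before baseline. A value used for screening could thus be up to 28 + 30 = 58 days old at baseline. Section 7.1 also has baseline labs repeated if they are more than 4 weeks old, but does not say that the 5.2 limits are applied again to that repeat. An acute condition could begin after the accepted sample was drawn.

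**Step 4: is there a backstop?** The physician-concern bullet in 5.2 is limited to adherence, and there is no general safety-discretion exclusion. The schedule in section 6 has medical history taken at screening and baseline, so a screener may learn of an obstruction, but 5.2 gives no criterion to apply to it.

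**Step 5: two related mismatches.** The label advice as reported in 12.2 covers biliary obstruction without qualification, while the exclusion in the same section covers only the acute form. Also, 12.2 names Cantabiline as the trial product, whereas 1.2 and 8.3 name Isochol 400 mg. Section 10.5 plans a comparison of the two products, so both appear to be relevant. The Isochol label text given in 9.4 lists undesirable effects only, so the documents do not show what that label says about biliary obstruction.

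**The case against.** The best reply is that this is silence and not a pair of opposing rules. Section 12.2 is part of the same protocol and says these patients will be excluded. Nothing permits their enrolment, and nothing says that the list in 5.2 is exhaustive. The laboratory limits act as an indirect screen. The trial is a single-site study of 16, and 9.14 requires study drug to stop when the investigator judges that to be in the participant's interest.

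Much of this stands, and it limits the consequence. It does not remove the mismatch: section 5 says candidates are screened against the criteria, and the other two exclusions in 12.2 do have counterparts in 5.2, at least in part. An omission is the more natural reading. If 12.2 is instead out of date, it still needs correcting.

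A reader might infer more than the documents support:

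- **That screening by 5.2 would enrol obstructed patients in general.** It would not. Anyone above one of the limits is excluded.
- **That participants have been told of this protection.** The consent pages are not available, so this cannot be seen. The point rests on the IRB's review.
- **That anyone wrongly enrolled would take H01 for 24 or 48 weeks.** That holds only for a participant allocated to H01 who does not stop. Under the 5:3 ratio in 3.1, 8.1 and 10.7, 3/8 of participants (16 × 3/8 = 6) would receive placebo in the blinded phase. One of these who entered the extension would have at most 48 − 24 = 24 weeks on H01.
- **That few or no candidates are affected.** The documents give no rate in either direction.

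**Conclusion.** The point holds as an internal inconsistency. An exclusion that 12.2 presents as a safety measure is missing from the criteria used for screening, and the related criteria in 5.2 cover it only indirectly. Screening by 5.2 could admit a candidate with biliary obstruction whose accepted labs are within the limits.

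The size of the gap cannot be stated. The documents give neither the frequency of biliary obstruction among candidates nor the share of such patients whose AST, ALT and bilirubin all stay at or below 2 × ULN.

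The conclusion assumes that screening staff work from section 5, as that section indicates, and that no separate screening form adds the criterion. It takes no position on which exclusion is clinically correct. The correction should be made because a safety exclusion is involved and the change is small, but the endpoints and the primary analysis are untouched.

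**What to change.** Reconcile 5.2 and 12.2 so that the screening list and the risk section state the same exclusion in the same words. Whether that is done by changing 5.2 or 12.2, and what the exclusion should be, is for the sponsor to decide.

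In the same amendment:

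- reconcile acute biliary obstruction, as excluded in 12.2, with the unqualified biliary obstruction in the label advice that 12.2 reports;
- reconcile the product named in 12.2 (Cantabiline) with the one named in 1.2 and 8.3 (Isochol), and make clear which label the risk text relies on;
- check that the consent form and any screening checklist agree with the reconciled text.

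The main change is about one line, and the product and label wording needs a few more. The amendment needs IRB review under 12.1. The sample size, randomization and analysis do not change.
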